	This will be a proof-of-concept, randomized, within-subject cross-over design with the administration of noise cancelling headphones or sham headphones on two separate study days. Following screening and a baseline assessment session with no headphones, participants will be assigned to complete each experimental session. During each session, they will undergo the CANTAB and Academic tasks. The order of sessions will be randomized and balanced across participants to be either noise-cancelling headphones first followed by sham headphones; or sham headphones first followed by noise-cancelling headphones.			

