#### Study Protocol

#### Recruitment & Randomization

30 children ages 6 to 18 will be recruited to participate.

Following a baseline assessment, participants will be randomized to receive 2 different sequences of experimental sessions (Noise cancellation headphones, then sham headphones; or sham headphones, then noise cancellation headphones). All participants will have a clinical diagnosis of ADHD and be willing to washout of any approved medication for 48 hours prior to the baseline and each experimental session.

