#### Baseline (Visit 2)

- Participants and their parents/caregivers will be assessed for any adverse events or changes in medical status since the last visit.
- Participants will complete the CANTAB ADHD battery with no headphones with standardized auditory distractors present. The CANTAB ADHD battery consists of the following subtests: Spatial Working Memory (SWM), Rapid Visual Information Processing (RVIP), and Stop Signal Task (SST).
- Participants will complete the Academic Productivity tasks for both math and reading comprehension with no headphones with standardized auditory distractors present.
- Participants will be fitted for the proper earbud size for headphones and practice inserting the earbuds.
- Participants will be randomized to one of the two experimental sequences and scheduled for Visit 3, to occur 7±3 days following the baseline visit.

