#### Power

The current study is powered to detect a "moderate" yet clinically relevant effect size estimate of 0.50. Sample size calculations assumed a 2-tailed statistical test of size  $\alpha=0.05$ , power  $1\text{-}\beta=0.90$ , approximate normality of the test statistic, no period effect, equal carryover effects between the two sequences, a correlation between groups of 0.60, and equal variances between groups. Under these assumptions, a sample size of 28 will allow us to detect a "moderate" standardized effect size of 0.50 between the noise cancelling headphone condition and the sham headphone condition on the primary scalar outcome of interest.

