#### Data Analysis

Data will be analyzed using SAS software, version 9.4 (SAS Institute Inc., Cary, NC, USA). Data will be tested for normality using the Kolmogorov-Smirnov 'Goodness of Fit Test.' For normally distributed data, *t*-tests will be used to compare outcomes between noise cancelling headphones and sham headphone controls; for data that are not normally distributed, Wilcoxon's test will be used. We will also investigate for the effects of sequence on the outcomes. This will be accomplished using analysis of variance (RMANOVA) with a within factor of 'noise cancelling headphones on first study visit' vs. 'noise cancelling headphones on second study visit.' Because of the use of multiple tests on the same set of data, alpha adjustment will be conducted in accordance with the Bonferroni-Holm procedure. We will also calculate Cohen's d values for all outcomes as an estimate for relevant effect size estimates for future studies. Missing data will be managed using standard multiple imputation procedures.

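### The sequence check declares randomized order a within-child factor, although each child has only one order; the model is wrong as written, but the fault is confined to this supplementary analysis

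*Combined protocol and SAP*

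**What the plan says.** The synopsis (Study Design) describes a "randomized, within-subject cross-over design" with two sessions and adds that "The order of sessions will be randomized and balanced across participants". Under Recruitment & Randomization, "participants will be randomized to receive 2 different sequences of experimental sessions": active then sham, or sham then active. Under Baseline (Visit 2), "Participants will be randomized to one of the two experimental sequences". Each child therefore completes both conditions, at Visits 3 and 4, in one order only.

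The Data Analysis section compares active with sham by t-test, or by Wilcoxon's test for non-normal data. It then turns to order: "We will also investigate for the effects of sequence on the outcomes". The method follows: "This will be accomplished using analysis of variance (RMANOVA) with a within factor of" active first versus active second (with the levels in full, "with a within factor of 'noise cancelling headphones on first study visit' vs. 'noise cancelling headphones on second study visit"). For this analysis the section names no between-child factor, no period (visit) term, no child term and no error term.

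**The concern.** The stated purpose (sequence) and the stated levels (active first, active second) agree with each other. Only the word *within* conflicts with them. No child has both levels, so no child supplies a contrast between them. In a two-period, two-treatment crossover, treatment and period vary within child, and sequence varies between children.

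At stake is the one planned analysis that bears on order effects. The Power section assumes no period effect and equal carryover in the two sequences. The Study Table of Assessments has the same CANTAB and academic measures at Visits 2, 3 and 4, so practice effects are plausible. As written, the check either cannot be run or can be coded in more than one way with different answers, which a pre-specified analysis should not allow.

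**Working it through.** **Plan's own figure.** The plan gives no figure for the sequence analysis. The sample size of 28 is used below only as an input. (It is not reproduced from its stated assumptions: 2(1 − 0.60) × [(1.960 + 1.282)/0.50]² = 33.6, so 34. That is a separate matter and nothing here depends on it.)

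**Inputs.** From the Power section: correlation ρ = 0.60, equal variances, two-sided α = 0.05, N = 28. From Recruitment & Randomization: 30 children to be recruited. Assumed: balance means 14 + 14 at N = 28, and the sequence test is judged at a nominal 5%.

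**Step 1: is sequence estimable within child?** With 28 child effects, period and treatment, the design matrix has rank 30. Adding a sequence column leaves the rank at 30, because that column is the sum of the indicators of the 14 children in one sequence. So sequence is not estimable within child. The treatment-by-sequence contrast is fully aliased with period (correlation −1.0): what varies within a child is the visit, not the order.

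**Step 2: the two error terms.** With variance σ² per score:
- child-within-sequence mean square: expectation σ²(1 + ρ)
- within-child residual mean square: expectation σ²(1 − ρ)
- ratio: (1 + 0.6)/(1 − 0.6) = 4

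**Step 3: false-positive rate with the wrong error term.** With no true sequence effect, MS(sequence) divided by the within-child residual is distributed as ratio × F(1, N − 2). At N = 28 the critical t on 26 degrees of freedom is 2.056, so the rate is P(|t₂₆| > 2.056/√4) = P(|t₂₆| > 1.028) = 0.314.

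| Assumed ρ | Ratio | N = 28 | N = 30 |
|---|---|---|---|
| 0.4 | 2.33 | 0.190 | 0.191 |
| 0.5 | 3.00 | 0.246 | 0.247 |
| 0.6 | 4.00 | 0.314 | 0.315 |
| 0.7 | 5.67 | 0.396 | 0.397 |
| 0.8 | 9.00 | 0.499 | 0.500 |

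**Step 4: simulation** (100,000 trials, 14 + 14 children, ρ = 0.60):
- sequence against within-child residual: 0.316
- all 56 observations treated as independent, child ignored: 0.127
- sequence against child-within-sequence (1 and 26 degrees of freedom): 0.050

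**Step 5: what the correct test can show.** Take a difference of 0.5 SD between sequences in the child's two-visit average, with SD that of a single score. The noncentrality is 0.5/√[((1 + 0.6)/2) × 4/28] = 0.5/0.338 = 1.48. Two-sided power is about 0.30 at N = 28 and 0.32 at N = 30.

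**The case against.** The strongest reply is that *within* is probably a drafting slip with little consequence. In a standard repeated-measures ANOVA, a variable that is constant within each child can only enter as a between-subject effect, and it is then tested against between-child variation. A mixed model with a random child effect does the same. Either gives 5%. If an analyst does try to fit sequence within child, the effect is not estimable and the problem shows at once. The 31% needs a particular choice: child fitted in the model and sequence tested against the residual. The 13% needs child to be ignored, which is not a repeated-measures ANOVA. All of this stands, and the inflation is therefore conditional.

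Three further qualifications also stand. The 0.60 is not said to refer to raw scores or to change from Baseline, so the range matters more than the single value. It is unclear whether the Bonferroni-Holm adjustment covers the sequence tests, so a 5% threshold per test is an assumption. And the correct test has low power, so even a proper version could not verify the equal-carryover assumption.

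A reader might infer that the headphone-versus-sham result is compromised. The documents do not support that, because neither the t-test nor the Wilcoxon test uses the sequence factor. A reader might also infer that a false sequence signal would change the primary analysis. No section makes any decision depend on the sequence result: there is no two-stage rule and no fallback to first-period data.

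What the reply does not remove is the text itself. It names a within factor and gives nothing that would lead to the right error term.

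**Conclusion.** The sequence analysis is wrong as written, at moderate severity. Order is assigned between children, so it is either not estimable within child or, if tested against within-child error, is tested at about 31% in place of 5% (ρ = 0.60, equal variances, 14 + 14 children, nominal 5% per test; 19% to 50% for ρ from 0.4 to 0.8). The mislabelling is certain from the text; the inflation is a worst case that depends on how the sentence is coded. It would go too far to say that the trial will often report a spurious sequence effect, because the plan fixes no error term and ordinary software practice would use the correct one. The defect stays within the supplementary sequence check and leaves the planned treatment comparison unchanged.

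**What to change.** Replace the sentence on the within factor with a model statement:
- sequence as a between-child fixed effect, tested against child-within-sequence variation (1 and 26 degrees of freedom at N = 28);
- visit (period) and treatment as within-child fixed effects;
- child as a random effect.

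Because this model contains its own treatment term, state that it is supportive and that the planned t-test or Wilcoxon test remains the primary comparison. Report the sequence estimate with its confidence interval as descriptive, and say that it will not be used to choose the primary analysis. Add that a non-significant sequence result will not be read as evidence of equal carryover.

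Changing *within* to *between* and naming the error term would cure the stated error on its own. The visit term is worth adding because it makes the period effect, which the Power section assumes to be absent, visible and estimable.

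The cost is a few sentences in the Data Analysis section and a few lines of SAS. No new data and no change to visits or sample size are needed.

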## PROTOCOL SYNOPSIS Bose-ADHD POC-001

Study Product	Bose QC Noise Cancelling Headphones/Earbuds			
Protocol Number	Bose –ADHD POC-001			
Protocol Title	A randomized, sham-controlled, crossover study to evaluate the effects of noise cancelling headphones on neurocognitive and academic outcomes in children and adolescents diagnosed with Attention Deficit Hyperactivity Disorder (ADHD)			
Sponsor	Bose			
Study Phase	Pilot/Proof of Concept			
Study Start Date	Q1 2017			
Study Centers	Number of Centers = 1 (Duke University, PI [name])			
Hypothesis	Children with ADHD will demonstrate better performance on neurocognitive and academic outcomes in the presence of auditory distractors while using Bose noise cancelling headphones compared to performance when using a sham device.			
Primary Objective	Evaluate performance on the ADHD Battery of the Cambridge Automated Neuropsychological Test Battery (CANTAB), including spatial working memory, inhibitory control, and attention while using either a noise cancelling headphone or sham headphone control in the presence of standardized auditory distractors.			
	
 
Compare change from Baseline scores on the CANTAB ADHD battery with noise cancelling headphones and sham-controls.
 
			
Secondary Objectives	Evaluate performance on academic productivity measures (math and reading comprehension) while using either a noise cancelling headphone or a sham headphone control in the presence of standardized auditory distractors.			
	
 
Compare change from Baseline scores on academic productivity measures with noise cancelling headphones and sham-controls.
 
			
	Evaluate subjective reports of experience using the noise cancelling headphones and sham-controls during the assessment tasks.			
_	Compare the self-reports of noise cancelling headphones versus sham controls.  Evaluate Safety			
	Evaluate any differences in self-reported adverse effects from using the noise cancelling headphones or sham controls.			
Study Design	Overview			

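### The stated 90% power at n = 28 does not follow from the plan's own inputs (81–84%), and it uses an unadjusted 0.05 for an unnamed primary score that the Holm rule, read literally, also covers

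*Combined protocol and SAP*

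**What the plan says.** **Power section.** "Sample size calculations assumed a 2-tailed statistical test of size" 0.05, with 90% power, a correlation of 0.60 between conditions, equal variances, no period effect and equal carryover. It concludes that 28 participants suffice for a standardized effect of 0.50 "on the primary scalar outcome of interest". It does not name that outcome and mentions no multiplicity adjustment.

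**Objectives (Protocol Synopsis).** The primary objective is a battery, "including spatial working memory, inhibitory control, and attention", with the instruction: "Compare change from Baseline scores on the CANTAB ADHD battery with noise cancelling headphones and sham-controls". The Baseline (Visit 2) and Experimental Sessions (Visits 3-4) sections list its three subtests, SWM, RVIP and SST, and choose no score or composite. The secondary objectives open with two academic measures: "Evaluate performance on academic productivity measures (math and reading comprehension".

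**Data Analysis section.** t-tests, or Wilcoxon's test for non-normal data, will "compare outcomes between noise cancelling headphones and sham headphone controls". Then: "Because of the use of multiple tests on the same set of data, alpha adjustment will be conducted in accordance with the Bonferroni-Holm procedure". The tests in the family are neither listed nor counted, and none is exempted. The section adds: "We will also calculate Cohen's d values for all outcomes".

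**Recruitment & Randomization.** Thirty children are to be recruited. No dropout rate is given.

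**The concern.** Two things do not fit together. The sample size in the Power section looks too small for its own inputs, before any multiplicity question arises. In addition, that section uses the full 0.05 for one score, while the Data Analysis section appears to put every tested outcome under Holm, where a single score may have to meet a stricter threshold.

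Because neither the score nor the family is written down, a reader cannot tell which result settles the primary objective or what threshold it must meet. The 90% figure would also mislead anyone weighing a null result: the chance of missing a true effect of 0.50 is at least 16–19% at n = 28, not 10%.

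**Working it through.** **Inputs (Power section):** two-sided alpha 0.05; power 0.90; effect 0.50 in units of the within-condition SD; correlation 0.60; equal variances; n = 28. Recruitment of 30 comes from Recruitment & Randomization. The comparison is taken as paired, as the within-subject crossover implies. Change from the single pre-randomization baseline does not alter the contrast, because the baseline cancels in the paired difference.

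**Step 1. Effect on the paired-difference scale.** SD of the difference = √(2 × (1 − 0.60)) = 0.894. So dz = 0.50 / 0.894 = 0.559 and dz² = 0.3125.

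**Step 2. Trying to reproduce n = 28.** n = ((1.960 + 1.282) / 0.559)² = 33.6, so 34 (normal approximation). The paired t-test needs 36. The stated 28 is not reproduced.

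**Step 3. Power at the stated n, two-sided 0.05.** Normal: Φ(0.559 × √28 − 1.960) = Φ(2.958 − 1.960) = Φ(0.998) = 84.1%. Paired t (noncentral t, 27 df): 81.4%. At n = 30: 86.5% (normal) and 84.1% (t).

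**Step 4. What would give 28.**
- One-sided 0.05 at 90% power: ((1.645 + 1.282) / 0.559)² = 27.4, so 28 (normal). This contradicts the stated two-tailed test.
- Two-sided 0.05 at 80% power by paired t: 28. This contradicts the stated 90%.
- Two-sided 0.05 at 90% power with a correlation of about 0.67 (normal) or 0.69 (t), or an effect of about 0.55 to 0.57. These contradict the stated 0.60 and 0.50.
- Taking 0.50 directly as dz moves further away: 43 (normal) or 44 (t) are needed, and power at 28 is 75% or 72%.
- Taking 28 per sequence (56 in all) gives 98–99%, which conflicts with recruiting 30.

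**Step 5. Primary score inside the Holm family.** The documents do not give the family size m, so these are assumptions: m = 3 (one score per CANTAB subtest) and m = 5 (adding math and reading).

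If only the given score responds, it must in effect pass 0.05/m. At n = 28:
- m = 3: Φ(2.958 − 2.394) = 71.4% (normal); 65.8% (t).
- m = 5: Φ(2.958 − 2.576) = 64.9% (normal); 57.9% (t).

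If every score has the 0.50 effect, later Holm steps help. Simulated Holm on paired t-tests at n = 28 (100,000 trials per setting) gives, for correlations between the outcomes' paired differences of 0 / 0.5 / 0.7:
- m = 3, a given score: 76.3% / 74.4% / 73.5%.
- m = 3, at least one rejection: 96.1% / 87.9% / 83.0%.
- m = 5, a given score: 70.9% / 68.9% / 68.1%.

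Holm never uses a threshold above 0.05, so power for a given score cannot exceed the 81–84% of Step 3, whatever m is.

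**The case against.** **It is a one-centre proof of concept that reports Cohen's d for every outcome.** True, and this limits the harm: estimates will accompany any missed threshold. But the plan itself chose a two-tailed alpha, a 90% power claim and Holm control, and those statements should agree with each other.

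**Under Holm, the chance of at least one significant score can exceed 90%.** Also true, for m = 3 when all scores respond and are weakly correlated. So a reader should not infer that no definition of success reaches 90%. The Power section, however, makes its claim for one scalar outcome, so this does not rescue it.

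**Family membership is settled by the text.** Largely so. A reader might infer that the primary score is equally likely to be inside or outside the family. The Data Analysis wording exempts nothing, so the literal reading puts it inside; only the unadjusted 0.05 in the Power section points the other way. The defect is the mismatch between the two sections, together with an unlisted family.

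**Post hoc choice is already controlled.** A reader might infer that the sponsor could freely pick a winning score after seeing the data. The documents do not support that: on the literal reading, Holm already covers selection among the tested scores. What stays open is which scores per subtest are tested at all, and hence m.

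**The t-test is not described as paired.** Correct. The 81% assumes pairing, which the design implies but the text does not state. The Wilcoxon branch and dropout were not modelled.

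**Conclusion.** The 90% figure is wrong as written. On the Power section's own inputs, n = 28 gives 84% (normal) or 81% (paired t), and 86% or 84% if all 30 are evaluable; 90% needs 34 or 36 completers. This shortfall does not depend on multiplicity. That 28 came from a one-sided calculation, or from an 80% target, is an inference; the documents do not say.

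Separately, the unadjusted 0.05 in the Power section conflicts with the literal scope of the Holm sentence, and neither the primary score nor the family is named. If the primary is in the family, power for a given score is lower again. For an assumed family of three at n = 28, it is 66% (t) to 71% (normal) if only that score responds and about 74–76% (t) if all three do. The lower range spans test method; the upper one spans correlation between outcomes. More than one score per subtest would enlarge m and lower both.

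This should be corrected before analysis, but it does not undermine the study's value as a pilot.

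**What to change.** Amend the analysis text before the data are analysed, with no added enrolment.

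1. **Define the primary test**, by one of two routes:
   - Name one CANTAB score, or one prespecified composite of SWM, RVIP and SST, and test it alone at two-sided 0.05. Apply Holm to the remaining outcomes or label them exploratory.
   - Name one score each for SWM, RVIP and SST as the primary Holm family, and state whether success means at least one significant score or a given one.
2. **Replace the 90% figure** with the power for that choice:
   - Single score tested alone: about 81–84% at n = 28 (84–86% at n = 30). For a composite, restate the effect and correlation assumed for it.
   - Three-score family at n = 28, given score: 66–71% (t to normal) if only it responds, 74–76% (t) if all three do.
   - Three-score family at n = 28, at least one score: 67% (t) if one responds, 83–96% (t) if all three do.

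Making the academic tests conditional on the primary result is optional. If the single-primary route is taken without that condition, the sponsor should know that the chance of any false rejection across five null outcomes is about 7–10% in simulation, against about 5% with it.

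Cost: a few sentences and one restated figure, with no change to visits, enrolment or data collection. The downside is committing to the score or scores in advance and stating a power below 90% for a given score.

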### **Study Table of Assessments**

	Screening	Baseline	Experimental Session 1	Experimental Session 2
Visit	1	2	3	4
Day	0	1-21	28 + 3	35 + 3
Informed consent and child assent	X			
Demographic & contact information	X			
Medical & Developmental History, including current medication status	Х			
MINI-Kid	X			
ADHD-RS	X			
KBIT-II	X			
Adverse Events	X	X	X	X
Concomitant Medications	X	X	X	X
Headphone Fit & Adjustment		X		
Randomization		Х		
Subjective Experience			Х	Х
CANTAB		X	X	X
Academic Productivity Measures		Х	Х	X
Study Debrief				Х
